### **3.5 Observational Phase**

Following randomization, participants will be followed for three months or more for the observation phase of the study. After three months and once the assigned dog from the Vendor has become available and been approved by the VA, the participant is eligible for the clearing visits. During the clearing visits, eligibility criteria will be verified, the assessments on functioning, mental health, psychosocial well-being and socioeconomic and health care utilization will be administered and a home visit will verify the home remains suitable for a dog.

### 3.6 Forms for Screening, Baseline, Observational and Clearing Visits

The following forms will be used during the screening visit, home visit, observational phase and clearing visit of the study.

*Table 1. Screening and Clearing Data Forms*

Form #	Form Name	Screening	Home/Baseline	Clearing Visit 1	Clearing Visit 2
	PHASE	0	0	1	1
	VISIT #	01	02	01	02
	Location	Clinic	Home	Clinic	Home
86	Informed Consent Confirmation	R			
1	Demographics	R			
2	Veteran Characteristics	R			
3	CAPS	R			
4	MINI	R			
5	Suitability for a Dog		R		R
7	WHO-DAS 2.0		R	R	
8	PCL		R	R	
9	PSQI		R	R	
10	VR-12		R	R	
11	C-SSRS	R		R	
12	PHQ-9		R	R	
13	DAR		R	R	
14	HERC Non-VA Utilization		R	R	
15	WPAI: GHP v2.0		R	R	
16	Inclusion/Exclusion & Randomization				R
17	Medication Log	A	A	A	A
18	Payment Log	A	A	A	A
25	Protocol Deviation	A	A	A	A
26	Adverse Events	A	A	A	A

26a	Adverse Events for Dogs	A	A	A	A
27	Serious Adverse Events	A	A	A	A
27a	Serious Adverse Events for Dogs	A	A	A	A
28	AE/SAE Follow-up	A	A	A	A
28a	SAE Follow-up for Dogs	A	A	A	A

R= REQUIRED

A = AS NEEDED

### 3.7 Follow-up

The primary objective of this study is to determine how the provision of a Service Dog or an Emotional Support Dog impacts function and quality of life for Veterans with PTSD. Primarily, the objective is to compare functioning and quality of life change, relative to baseline, over the 18-month intervention period between the two groups of Veterans with PTSD, i.e., those who receive Service Dogs and those who receive Emotional Support Dogs. The secondary outcomes in this study are: 1) a reduction in PTSD symptoms as measured by the PTSD Civilian Checklist (PCL); 2) improvement in depression as measured by the PHQ-9; 3) improvement in sleep as measured by the Pittsburg Sleep Quality Index (PSQI); 4) decreased thoughts of suicide as measured by the Columbia-Suicide Severity Rating Scale (C-SSRS); and 5) to characterize and compare how healthcare costs and utilization are impacted. All primary and secondary outcome measures will be collected at baseline, clearing, and at 3, 6, 9, 12, 15 and 18 month post-pairing. The following forms will be used during the follow-up phase of the study.

Table 2. Follow-up Phase Data Forms

Form #	FORM Name	1 week	2 week	1 month	2 month	3 month	6 month	9 month	12 month	15 month	18 month
	PHASE	2	2	3	3	3	3	3	3	3	3
	VISIT #	01	02	01	02	03	06	09	12	15	18
	LOCATION	Home	H/P	Home	H/P	Clinic	Home	Clinic	Home	Clinic	Home
3	CAPS										R
7	WHO-DAS 2.0					R	R	R	R	R	R
8	PCL-5					R	R	R	R	R	R
9	PSQI					R	R	R	R	R	R
10	VR-12					R	R	R	R	R	R
11	C-SSRS					R	R	R	R	R	R
12	PHQ-9					R	R	R	R	R	R
13	DAR					R	R	R	R	R	R
14	HERC Non-VA Utilization					R	R	R	R	R	R
15	WPAI: GHP v2.0					R	R	R	R	R	R
17	Medication Log	A	A	A	A	A	A	A	A	A	R
18	Payment Log	A	A	A	A	A	A	A	A	A	R
19	Post Pairing Evaluation	R	A	A	A	A	A	A	A	A	A
20	Veteran and Service/ES Dog Visit Report	R	A	R	A	A	R	A	R	A	R
21	Dog Related Questions	R	R	R	R	R	R	R	R	R	R
22	Dog Return	A	A	A	A	A	A	A	A	A	A
23	Veterinarian Checklist	R					R		R		R
24	Study Completion/Termination	A	A	A	A	A	A	A	A	A	R
24a/b	Exit Interview – SERV or Exit Interview – EMOT										R
24c	Dog Trainer Evaluation										R
25	Protocol Deviation	A	A	A	A	A	A	A	A	A	A
26	Adverse Events	A	A	A	A	A	A	A	A	A	A
26a	Adverse Events for Dogs	A	A	A	A	A	A	A	A	A	A
27	Serious Adverse Events	A	A	A	A	A	A	A	A	A	A
27a	Serious Adverse Events for Dogs	A	A	A	A	A	A	A	A	A	A
28	AE/SAE Follow-up	A	A	A	A	A	A	A	A	A	A
28a	SAE Follow-up for Dogs	A	A	A	A	A	A	A	A	A	A

H/P = HOME/PHONE

R = REQUIRED

A = AS NEEDED

### 3.8 Sample Size

The goal for this study is a sample size of 220 including adjustment for subjects who withdraw or are lost-to-follow-up and interim analyses. In order to detect a 15% difference in mean scores for MCS (outcome requiring largest sample) over the 18-months of follow-up, at a statistical significance level of 0.05 (two-tailed test) and a power of 0.85, 82 participants per group will be needed, and 110 participants per treatment (220 total) will be required to account for a maximum of 25% post-pairing participant loss or dropout rate (see protocol). This sample size results in an expectation of 110 subjects in each of the treatment groups. For challenges in the recruitment of participants or in the pairing (or availability) of dogs, sample size will be revisited and adjusted accordingly taking into account the study's post-pairing termination rate. For 80%, a sample size of 72 per group is needed, and 90 participants per treatment (180 total) to account for a 20% post-pairing termination rate or 85 (170) to account for a 15% termination rate. When such challenges occur, a sample size of 180 will be the aim.

The Statistical Programmer is responsible for the preparation of the tables and analyses for all of the routine study reports. These include Study Group, Executive Committee, Data Monitoring Committee, and the mid-study report to CSSEC. S/he also prepares the tables and reports for the final analyses. S/he works closely with the Biostatistician on these analyses.

The Database Management System (DBMS) Programmer is the lead of the data management support group and works closely with the assigned computer assistant(s) to address the data management need for the assigned study. S/he is responsible for establishing, updating and maintaining the study's database. In addition, s/he will write edit program based on an agreed upon edit plan that will thoroughly check the data for errors and missing information. S/he is also responsible for programming and maintaining the randomization system for the study.

The Computer Assistant(s) are responsible for setting up the data definition table for the study, for building the Study Definition Editor and also for laying out the electronic case report forms in the form design software. They are also responsible for training the study staff at each site on how to properly manage the data collection process and how to appropriately respond to data edits. The computer assistant(s) are also responsible for working with the sites to resolve the data queries generated based on the incomplete and/or inaccurate data submitted to the study database.

## 4.2 Data Management

The data management system for this study will be built using DataFax. Each site will fax completed data collection forms to the CSPCC where they will be reviewed and validated. When a fax arrives at the CSPCC, DataFax breaks it into pages and proceeds to process each page. It identifies which study each page belongs to, reads the data from each page, enters the data into the study database, and stores all pages. CSPCC Computer Assistants use split-screen validation to review all pages received, complete data entry, and flag any problems they identify (e.g., missing data) with Quality Control (QC) notes. Randomization will be completed at the Perry Point CSPCC using ENVOX, an automated interactive telephone system.

Tables 1 and 2, above, list the case report forms and the assessments that will be used in this study and indicates when each will be administered. The Local Site Investigator (LSI), Study Coordinator (SC) or other local study team members at each participating site will record participant data on the study

---

forms. The final responsibility for the completeness and accuracy of all study data collected at a participating site resides with the LSI. After checking the forms for completeness and accuracy, the LSI or other designee will be required to sign and date each form. Data forms are faxed to the Perry Point CSPCC where data are processed and data checks are implemented to prevent errors and to prompt the sites for resolution. Data will be transmitted directly to the CSPCC improving the ability to monitor site progress and the status of the trial and participants.

When a participating site has a potential study participant that meets all of the eligibility requirements, the LSI or SC (or other local study team member designee) will assign a unique participant ID and Alpha code to the participant. This unique Participant ID number and alpha code will be entered on all study related forms for the duration of the study. Examples of study-related forms include the participant's data collection forms, data quality reports, etc. for the remainder of the study.

The DataFax system will have built-in edit checks on data fields to minimize data errors, such as missing, inconsistent, or extremely unusual data. The data management staff at the coordinating center will generate data query forms which will be sent to the sites for clarifications. The study database will be continuously updated with new data and changes to previously submitted data. To notify the participating sites about missing or late forms, reports with pertinent information will be generated at a regular interval and will be posted on the study SharePoint site.

In addition, a summary report of all data submitted and problems identified will be generated for each participating site. This report will provide each site with a summary of their progress. The National Study Coordinator in the Chairman's Office will also be reviewing each site's progress to ensure that there are no unforeseen problems with the forms or with a particular participant.

## 5 GENERAL CONSIDERATIONS

### 5.1 Timing of Analyses

The Study Group (all of the LSIs) and Executive Committee will meet six to nine months after participant recruitment begins and at annual intervals thereafter until the end of the study. Three weeks prior to these meetings and at six-month intervals between the meetings, these groups will be provided a report that will allow them to assess study progress. These reports will contain information on:

- Screening, Enrollment and Retention
- Participant background characteristics at entry
- Data quality and protocol adherence
- Participant characteristics during observation phase

Reports will be created for the Data Monitoring Committee starting approximately six months after the official start of the study. Data monitoring committee reports will be created every six months thereafter.

The final analysis will be performed on data which will have been documented as meeting the cleaning and approval requirements of CSP SOPs and after the finalization and approval of this SAP document.

## 5.2 Analysis Populations

The exact process for assigning the statuses will be defined and documented prior to final analyses along with any predefined reasons for eliminating a subject from a particular population.

### All Study Participants

This population includes all participants who signed the informed consent form to participate in the study.

### Intent-to-Treat (ITT)

This population includes all subjects who are randomized to the study.

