In some cases, the study dog will need to be permanently removed from the participant with no option of a replacement dog. Reasons for permanent removal include the inability to resolve the issues surrounding a temporary removal in a timely manner, the participant refuses a replacement dog, the participant withdraws early from the study due to personal reasons, or the participant is terminated early from the study by research staff due to study related ineligibility.

Participants may be eligible to continue in the study once their study dog has been permanently removed. The local LSI and other study leadership, including the study Chair and CMVO, will be consulted to determine eligibility for continued follow up. Participants who remain in the study will be encouraged to complete all follow-up assessments because follow-up data are important to the validity of the study results and for future patient care.

Participants who agree to follow up visits after the permanent removal of their study dog will complete all visits in the clinic, receive an incentive payment of \$25 for each visit, will not be required to complete dog related components (dog surveys, public observations, and veterinary exams), and will no longer receive the \$75 dog care stipend. If at any time the participant requests to be withdrawn from the study or completes the final 18 month visit, the participant will be withdrawn from the study.

Participants who agree to follow-up visits in the absence of a study dog and agree to complete the Exit Interview should be administered the interview based on the following guidelines:

1. At the permanent dog removal visit (i.e., removal is considered permanent at the time of removal), or
2. By phone within approximately 2 weeks of the permanent dog removal visit or after the decision to permanently remove the dog has been made (i.e., temporary removal resulting in a permanent removal), or
3. During the next scheduled study visit following the permanent dog removal visit or after the decision to permanently remove the dog has been made (i.e., temporary removal resulting in a permanent removal), or
4. Participants in follow-up without a study dog at the time of this update: by phone at the participant's earliest convenience or during the next scheduled study visit instead of waiting until the final study visit.

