 - has skin sores that cannot be explained by a medical condition
 - has gross parasite infection (fleas, ticks)
 - has any other conditions that suggest it has been neglected or abused
- h. Dog health issues/care of dog diminishes: There is evidence that the participant cannot adequately care for their dog.
- i. Lack of ongoing treatment: participant stops receiving ongoing mental health treatment (i.e., PTSD treatment).
- j. Lack of veterinarian care: participant does not schedule and honor the veterinarian visits that are required by the study or they do not take their dog to a veterinarian for treatment if it is sick or injured.

- k. Participant death.
- l. Participant no longer meets study criteria (i.e., incarceration, not accepting the outcome of the dog randomization, family refuses study dog, substance abuse, not able to travel to the vendor (SD group), participant does not follow through with study related requirements, etc.).
- m.
- n. Engaging in a relationship with vendor: participant donates to, works for, or volunteers with a vendor providing dogs while they are still in the study.
- o. No secondary dog caregiver during intermittent absences: participant does not have someone who is able to care for their dog during short term absences.
- p. Dual enrollment in an unapproved study.
- q. Obtains outside training for their study dog: While in the study, participant-initiated training of study dogs by outside sources is prohibited. All training needs will be met by the designated vendor and VA dog trainers (local or national).
- r. Not reporting aggressive behaviors or displays of aggression by the dog.

1. Pre-pairing Terminations

If study team members have concerns about a participant's eligibility prior to pairing, they should consult with the LSI. If the LSI has questions about the participant's status they can consult with the study Chair to help make a determination. Additional leadership will be consulted by the LSI and Chair as needed.

2. Post-Pairing Terminations

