In order to detect a 10-point difference in treatment group mean scores for the WHO-DAS 2.0 over the 18 months of follow-up, at a statistical significance level of 0.05 (two-tailed test) and a power of 0.85, 32 participants per group will be needed (see Table 6). In order to detect a 15% difference in mean scores for MCS over the 18-months of follow-up, at a statistical significance level of 0.05 (two tailed test) and a power of 0.85, 82 participants per group will be needed (see Table 6). In order to detect a 15% difference in mean scores for the PCS over the 18-months of follow-up, at a statistical significance level of 0.05 (two tailed test) and a power of 0.85, 60 participants per group will be needed (see Table 6). The sample size estimates were obtained using the PC-software SAS 9.2.

Assuming the largest of the three sample sizes, 82 participants per group, and a maximum of 25% participant loss or dropout rate a sample size of 110 participants per treatment will be required for this study. To obtain the necessary sample size of 220 participants, at least three VA medical centers will be recruited. Once a participant has been determined to be eligible for the study at the participating VA medical center, randomization to one of the two groups will be accomplished by a telephone call to the Perry Point Coordinating Center. All sites will be encouraged to recruit and enroll participants faster than the stated requirements.

- **Statistical Methods**

The intent-to-treat population (ITT) is defined as the population of participants who will be randomized in either the Service Dog (SERV) or Emotional Support Dog (EMOT) treatment groups. The participants will be categorized based on their initial randomized group assignment and will be included in analyses irrespective of their status – completer or drop out of the study before completion. A per protocol population (PP) is defined as the population of participants who are paired with a dog. Analyses of all outcome measures – primary and secondary – will use both the ITT and PP population.

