### Per-Protocol Population (PP)

This population includes all participants who are paired with a dog.

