## 5.3 Missing Data and Imputations

The primary analyses will analyze the data as observed.. In the hopefully unlikely event that a dog needs to be replaced after pairing (e.g., dog dies, gets hurt, becomes aggressive), then the participant's data will be included in the analysis up to this point. The participant will still be offered another dog and will remain enrolled in the study for the remainder of the 18 months. Data will be collected after the dog has been replaced, however it will not be used in the primary analysis.

However, some missing data will arise. When missing data are encountered in the analyses and considered substantial, a detailed sensitivity analysis will be conducted on the effects of various assumptions about the missing data. Within the taxonomy of Little and Rubin, mechanisms will be a mixture of missing completely at random (MCAR), missing at random (MAR), or missing not at random (MNAR). MAR assumes that missing status is due purely to observed variables while MNAR allows missing status to also depend on the value of the missing datum. An example of MCAR is when a participant moves away. The sensitivity of results to assumptions about the missing-value mechanism

(MAR and MNAR) will be examined by analyzing the data with methods appropriate to each. Multiple imputation will be performed under the assumption that missing data are MAR (Little and Rubin, 2002). Assuming MNAR, we will fit the data to pattern-mixture models, assessing sensitivity to various identifying restrictions, as needed (Thijs et al., 2002).

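### For WHODAS, PCS and MCS the ITT and per-protocol analyses give practically the same estimate by construction, and loss between unblinding and pairing is not shown by arm

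*SAP*

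**What the plan says.** SAP 5.2 defines the ITT set in one sentence, "This population includes all subjects who are randomized to the study", and the per-protocol (PP) set in another, "This population includes all participants who are paired with a dog". PP carries no adherence criterion. Protocol XVIII, Statistical Methods, adds that ITT participants "will be included in analyses irrespective of their status" and applies both sets to every primary and secondary outcome.

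The order of events comes from Protocol VII, VIII and X and SAP 3.4, 3.5 and 3.7:

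- Randomization is followed by an observation phase of three months or more. Protocol VII (Preliminary Screening) leaves eligibility open until placement or pairing is complete.
- WHODAS 2.0 and VR-12 are taken at Baseline 1 and again at Baseline 2 (clearing).
- Participant and site learn the dog type after the Home Clearing visit and before pairing.
- The outcome visits at months 3 to 18 are counted from receipt of the dog.

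SAP 5.3 states: "The primary analyses will analyze the data as observed". Multiple imputation and pattern-mixture models follow only if missing data are judged substantial, and no threshold is given. Protocol XII lists among its grounds for termination "not accepting the outcome of the dog randomization, family refuses study dog, substance abuse, not able to travel to the vendor (SD group"). SAP 6.1 promises completion and discontinuation after randomization for each treatment group.

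**The concern.** An ITT analysis protects the comparison because everyone randomized contributes an outcome, whatever happens afterwards. Here the never-paired have no outcome in the period being compared. The label says all randomized; the treatment estimate comes from those who were paired.

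Two things are at stake. First, reporting ITT beside PP invites the reader to take agreement as a sign that attrition did no harm, when the two analyses share all their post-pairing data. Second, between unblinding and pairing the participant knows the arm, and the burdens differ: Protocol IX describes one to two weeks at a vendor's site for a Service Dog (SERV) against one to two days at home for an Emotional Support Dog (EMOT). Loss in that window can depend on arm, and neither set corrects for it.

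**Working it through.** **1. The plan's own figure.** Inputs are from Protocol XVIII Table 6 and SAP 3.8: MCS mean 33.2, SD 10.6, a "15% difference in mean scores for MCS (outcome requiring largest sample"), and "at a statistical significance level of 0.05 (two-tailed test) and a power of 0.85, 82 participants per group will be needed".

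- Target difference: 0.15 × 33.2 = 4.98 points.
- n per group = 2 × (1.960 + 1.036)² × 10.6² / 4.98² = 81.4, so 82.
- 82 / 0.75 = 109.3, so 110 per arm and 220 in total.

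The figure reproduces. The 25% allowance covers loss after pairing, and Protocol V counts the 220 as paired. Nothing is allowed for loss between randomization and pairing. About 300 are to be consented, so (300 − 220) / 300 = 26.7% are lost from consent to pairing. The part falling after randomization is not given.

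**2. Who supplies which score.**

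| Randomized Veteran | Baseline 1 | Baseline 2 (clearing) | Months 3–18 | In ITT | In PP |
|---|---|---|---|---|---|
| Lost before clearing | yes | no | none | yes | no |
| Lost after unblinding, never paired | yes | yes | none | yes | no |
| Paired | yes | yes | yes, while followed | yes | yes |

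The sets differ only in pre-pairing rows.

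**3. How much those rows matter.** Simulation with assumed inputs: 150 trials, 110 randomized per arm, no true effect, one pre-pairing score and six later ones. Starting mean 33.2; SDs are 8 (person), 5 (unobserved response) and 4.8 (visit), about 10.6 overall. SERV loses 20% and EMOT 5% before pairing, with loss correlated 0.5 with the unobserved response.

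| Model | ITT as observed, mean | PP, mean | Correlation | Largest gap in one trial |
|---|---|---|---|---|
| Random intercept, common baseline mean | 0.589 | 0.589 | 0.99998 | 0.02 |
| Random intercept, baseline mean by arm | 0.585 | 0.576 | 0.993 | 0.37 |
| Baseline as covariate | 0.594 | 0.594 | 1 | 0 |

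The true difference is zero, so all of these are selection bias, and ITT carries as much of it as PP. The SAP does not fix how baseline enters the model. Whichever form is used, the two sets agree closely.

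**4. Size of a possible bias.** If an arm loses a fraction p, and those lost would have scored lower than the paired by a gap D, the paired mean exceeds the mean of all randomized by p × D. With loss p in one arm, q in the other and the same gap, bias = (p − q) × D. Losses and gaps below are assumptions.

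- 15% against 5%, gap 1 SD: 0.10 × 10.6 = 1.06 points; 1.06 / 4.98 = 21% of the target.
- 10% against 5%, gap half an SD: 0.05 × 5.3 = 0.27 points; 0.27 / 4.98 = 5%.

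The sign depends on which arm loses more and on who leaves.

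**5. What the shells show.** SAP Table 5 gives randomized participants only as in the observation phase or paired, by site. SAP Table 7 splits by dog type only in its two dog-type columns. It has no column for discontinued, no arm split before pairing, and no division of loss at unblinding.

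**The case against.** The case for the plan is substantial, and it rules out several stronger readings.

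- A reader might infer that post-randomization losses go unrecorded. They do not: SAP 6.1 commits to discontinuation by treatment group, and Protocol Table 5 requires the completion/termination form for all randomized participants. What stands is that the shells do not deliver that commitment by arm or by stage.
- A reader might infer that a never-paired Veteran has no outcome after randomization. The clearing visit records WHODAS and VR-12 after randomization, before participant and site know the arm. It says nothing about the period with a dog.
- A reader might infer that modelling baseline and clearing scores as responses would restore ITT. The first two models in the working keep a pre-pairing score in the response, and the bias is unchanged.
- Entry criteria 9 and 12 (accepting the randomization result; willing and able to travel if assigned a Service Dog) target the two arm-related exits. They reduce them, but Protocol XII still lists both as grounds for termination.
- Loss before Home Clearing cannot be driven by participant or site knowledge of the arm.
- SAP 5.3 does plan missing-at-random and not-at-random analyses, but conditionally and without naming the never-paired.
- Cost and utilization run by quarter from enrollment, by intended treatment, from VA administrative data (Protocol XIV and XVIII). The problem does not extend to them.

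The bias figures are also hypothetical. They use the raw SD, although the outcomes are baseline-adjusted.

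**Conclusion.** The point holds for WHODAS 2.0, PCS and MCS. The stated ITT set cannot deliver what Protocol XVIII claims for it, because the visit schedule gives the never-paired no follow-up outcome. ITT and PP will agree whether or not pre-pairing loss has biased the comparison.

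That rests on the documents alone. The size of any bias does not: 0.27 to 1.06 MCS points depends on assumed losses and gaps, and if loss is equal in the two arms with the same gap the formula gives zero. The documents support neither a claim that the comparison is biased nor a claim that it is safe. They show that the planned ITT/PP pair cannot tell the two apart, and that the planned tables would not reveal which applies. This should be corrected before the final analysis.

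**What to change.** 1. In SAP 5.2 and 7.1, call the efficacy set for these three outcomes *randomized and paired (modified ITT)*, and state that agreement with PP will not be presented as a robustness check. SAP 5.2 already leaves the assignment of population status to be documented before final analysis.
2. Revise SAP Tables 5 and 7 to give, by arm, the numbers randomized, unblinded and paired, with reasons for loss from randomization to unblinding and from unblinding to pairing. The termination form covers everyone needed.
3. In SAP 5.3, make a delta-adjusted (missing-not-at-random) multiple-imputation analysis mandatory. It should include all randomized, never-paired Veterans, with deltas fixed in advance and varied separately by arm, whether or not missing data are judged substantial.

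The cost is SAP wording, one fuller table, one more analysis and a less favourable label. No new data are needed.

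Following never-paired Veterans is optional. Protocol XI has a model for follow-up without a dog ("Participants who agree to follow up visits after the permanent removal of their study dog will complete all visits in the clinic"), but that schedule runs from receipt of a dog. Extending it would need a defined time zero and a protocol amendment. Protocol II also reports that Veterans in the original study who no longer wanted a dog were unwilling to be followed.
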